### **Blood draw**

#### **Rare (1-10%)**

- Bleeding
- Pain
- Bruising
- Redness, swelling of the vein
- Infection
- Fainting

### **MRI**

May cause a metal object in your body to move out of place and cause serious injury or stop working properly [7]

### **2.3.2 Mitigation of Risks**

Standard subject safety precautions will be employed for the procedures listed above, per institutional guidelines and best practice.

## **3.0 Objectives and Endpoints**

### **3.1 Primary Objective**

The primary efficacy co-outcomes are: a change in the visual analog scale (VAS) pain score and a change in the pain subsection of the knee injury and osteoarthritis outcome (KOOS) score.

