#### **9.3.2 Primary and Secondary Efficacy Analyses**

Eight separate repeated-measures analysis will be performed on the eight efficacy variables described above. Each of the eight variables will be used as a dependent variable. The following model building method will be used for each analysis. Using Statistical Analysis System (SAS) MIXED Procedure (version 9.4; SAS Institute, Cary, NC), a linear mixed model will be fit on each efficacy variable. The model will include site, treatment arm, time on study (baseline and 1, 3, 6, 9

and 12 months on study), and treatment arm by time interaction as fixed effects. Subject ID will be the random effect. A compound-symmetric variance-covariance form in repeated measurements will be assumed and robust estimates of the standard errors of parameters will be used to perform statistical tests and construct 95% confidence intervals. The model-based means are unbiased with unbalanced and missing data, assuming missing data are non-informative. A P-value  $\leq 0.05$  will be considered statistically significant for all the terms in the mixed model. The statistical test for interaction between time on study and treatment will be the overall hypothesis test to determine whether efficacy variables in the four treatment arms changed significantly during 12 months of follow-up. If mean scores in the treatment arms are consistently different or similar over time (i.e., no statistical interaction) then the main effect test for treatment will be used as the primary hypothesis test to compare the treatment arms. The primary study results from this model will be the mean score and 95% confidence interval for each of the 4 treatment arms and the treatment mean differences and 95% confidence intervals.

Assuming a significant treatment effect on efficacy score change is identified (i.e., the interaction test is significant at  $P = 0.05$ ) then the six pairwise treatment comparisons on pain score change will be performed. A Bonferroni correction ( $p=0.05/6=0.0083$ ) for multiple comparisons will be applied. Specific statistical tests on efficacy score change will be done within the framework of the mixed effects linear model. All statistical tests will be 2-sided and adjusted for multiple comparisons. The same Bonferroni method will be used if the statistical interaction between treatment group and time on study is not significant but the main effect test for treatment is significant.

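### The plan names two primary outcomes but no success rule: its 0.05/6 cut covers one outcome's pairs, so 5% is not held if either suffices, and the chance of success is unstated if both must

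*Combined protocol and SAP*

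**What the plan says.** Section 3.1 gives two primary outcomes: "The primary efficacy co-outcomes are: a change in the visual analog scale (VAS) pain score and a change in the pain subsection" of KOOS. The synopsis and sections 9.2 and 9.3.1 also name both as primary.

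Section 9.3.2 handles each outcome on its own: "Eight separate repeated-measures analysis will be performed on the eight efficacy variables described above". A P-value at or below 0.05 "will be considered statistically significant for all the terms in the mixed model". If the treatment-by-time interaction is significant, "then the six pairwise treatment comparisons on pain score change will be performed", with the threshold "p=0.05/6=0.0083". There is a fallback: "The same Bonferroni method will be used if the statistical interaction between treatment group and time on study is not significant" but the treatment main effect is. The section also says: "All statistical tests will be 2-sided and adjusted for multiple comparisons". The only adjustment it specifies is the division by six.

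Section 9.2 gives 91% power for VAS and 97% for total KOOS, each outcome alone, at two-sided 5% with 121 per group. Total KOOS stands in for KOOS Pain. The same section plans 30 subjects per group at each of four sites and expects 90% retention at one year.

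**The concern.** Four groups give six pairs, so two primary outcomes give 12 primary pairwise tests. A divisor of six protects one outcome's family. The plan never says whether a comparison is positive when one outcome passes or only when both do.

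The gap has consequences under either rule. If one outcome is enough, the correction does not deliver the 5% it appears to promise. If both are needed, the two separate powers in section 9.2 do not give the chance that the trial meets its own criterion. If VAS and KOOS Pain disagree, the rule could be chosen after the data are seen. That matters in a phase 3 trial meant to pick a superior cell source and validate it against corticosteroid.

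**Working it through.** **Inputs.** From section 9.2: VAS difference 1.5, SD 3.5; total KOOS difference 10, SD 20; 121 per group in the calculation; 4 × 30 = 120 per group enrolled; 90% retention, so 0.9 × 120 = 108. From section 9.3.2: overall test at 0.05, then six pairs at 0.05/6. The correlation between the two outcomes is not in the documents. It is assumed, over 0 to 0.9.

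**Reproducing the stated power.** With z = difference / (SD × √(2/n)) and power = Φ(z − 1.96), at n = 121:
- VAS: z = 1.5 / (3.5 × 0.1286) = 3.33, power 91.5% (noncentral t 91.3%).
- Total KOOS: z = 10 / (20 × 0.1286) = 3.89, power 97.3% (noncentral t 97.2%).

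Both stated figures reproduce.

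**If either outcome suffices.** Simple bounds first: 12 × 0.05/6 = 10%, and two independent 5% overall tests give 1 − 0.95² = 9.75%. A large-sample simulation under no true differences then used four groups, two outcomes, one 5% overall test per outcome followed by its six pairs at 0.05/6, and 1,000,000 trials per correlation.

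| Correlation | 0 | 0.5 | 0.7 | 0.8 | 0.9 |
|---|---|---|---|---|---|
| One outcome, any false pair after overall test | 3.8% | 3.8% | 3.8% | 3.7% | 3.8% |
| Either outcome, any false pair after overall test | 7.4% | 7.0% | 6.5% | 6.1% | 5.5% |
| Either outcome, any false pair, no overall test | 8.1% | 7.7% | 7.2% | 6.7% | 6.1% |
| Either outcome, false overall test | 9.7% | 9.2% | 8.5% | 7.9% | 7.2% |
| Either outcome, any false pair at 0.05/12, no overall test | 4.3% | 4.1% | 3.9% | 3.6% | 3.3% |

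One outcome alone stays below 5%, so the excess comes from the second outcome. A cut of 0.05/12 removes it.

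**If both outcomes are required.** A false claim for a pair then needs the null outcome to pass at 0.0083, so six pairs give at most 6 × 0.0083 = 5%. No further split is needed. For power, the two-sided critical value at 0.05/6 is 2.638. At n = 108:
- VAS: z = 1.5 / (3.5 × 0.1361) = 3.15, power Φ(0.51) = 69.5% (noncentral t 68.6%).
- Total KOOS: z = 10 / (20 × 0.1361) = 3.67, power Φ(1.04) = 85.0% (noncentral t 84.3%).
- Both, bivariate normal: 59.1% at correlation 0 (0.695 × 0.850), 63.8% at 0.5, 66.1% at 0.7 and 68.8% at 0.9.

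With no attrition (n = 120) the joint figure is 67-75%.

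**Where the loss arises (normal approximation).**
- VAS at 0.05, n = 121: 91.5%.
- Threshold changed to 0.0083: 75.7%, a loss of about 16 points.
- n reduced to 108: 69.5%, a further 6 points.
- Both outcomes required: 63.8-66.1% at correlation 0.5-0.7, a further 3-6 points (about 1-10 points over 0 to 0.9).

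As a cross-check, joint power at 0.05 and n = 121 is 89-91%, close to the stated VAS figure.

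**The case against.** Calling the two measures co-outcomes and joining them with a conjunction may mean that both are required. If so, the error rate across outcomes is not inflated. That stands as a possible intention, but the wording does not settle it and no decision rule follows from it. A reader might infer that the plan allows a claim on VAS or KOOS Pain alone, so that inflation is certain. The documents do not say that one outcome suffices; they are silent.

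A reader might also infer that having two primary outcomes is what pulls power from 91% and 97% down to the mid-60s. The arithmetic does not support this. About 22 of the roughly 26 points lost from the VAS figure come from the 0.0083 cut and attrition, and would be lost with a single primary outcome.

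The simulation is simpler than the plan. It uses one overall test per outcome, whereas section 9.3.2 tests the interaction over six time points and then falls back on the main effect. The fallback is a second way through the gate and was not modelled, so the error rates are approximate. The larger 7-10% figures concern the overall test, which names no superior treatment. At correlations of 0.7 to 0.8 the pairwise excess over 5% is only about 1.1 to 1.5 points.

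Finally, section 9.3 calls itself a summary of a SAP that has been developed, and section 9.3.2 says all tests are adjusted. A rule could stand in a fuller SAP. None appears in the text available, and the one adjustment described is over six pairs.

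**Conclusion.** The point holds in conditional form. The two primary outcomes have no stated success rule, and 0.05/6 fits only one of the two possible rules.

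- **Either suffices:** any false pairwise claim occurs in about 7.4% to 5.5% of trials for correlations 0 to 0.9. This is a moderate excess that shrinks as the correlation nears 1.
- **Both required:** error is controlled, but the success probability per pair is about 59-69% with 108 per group (64-66% at correlation 0.5-0.7) and is stated nowhere.

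Only one of these applies, depending on the rule. The figures rest on an assumed correlation, on total KOOS as proxy for KOOS Pain, on the one-year t-test of section 9.2 in place of the mixed model, and on a single overall test per outcome. The absence of a rule depends on none of these.

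**What to change.** In section 9.3.2, state one of two rules before unblinding:
- A treatment comparison is positive only if the changes in both VAS and KOOS Pain are significant for the same pair at 0.0083. No further alpha split is needed. This is the simpler choice.
- If either outcome is to suffice, test the 12 primary comparisons at 0.05/12 = 0.0042, or by Holm over the 12.

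In section 9.2, restate power at the threshold actually used and with 90% retention. Under the first rule, give joint power as a range (59-69% at 108 per group), with the correlation and the total-KOOS proxy marked as assumptions. Under the second, at 0.0042 and 108 per group, VAS alone has 61% and total KOOS 79%. At least one succeeds with probability 61.2 + 79.1 − 54.3 = 86% at correlation 0.5, or 61.2 + 79.1 − 57.1 = 83% at 0.7.

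The cost is a short addition to the text and a less favourable stated power. No change in enrolment is needed to make the rule clear. Keeping VAS alone at 91% at 0.0083 would be a separate decision: about 173 evaluable, or 193 randomised, per group (173 / 0.9).

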### **3.2 Secondary Objectives**

Secondary outcomes include change in total KOOS score, EuroQuality of Life (EQ5D 3L) and Patient-Reported Outcomes Measurement Information System (PROMIS 29).

Changes in MRI biomarkers of cartilage and joint health between the four treatment groups will be compared.

### **3.3 Exploratory Objectives**

To provide deep and broad characterization of all cells used in this trial, harmonize and standardize analytical and processing parameters across the different clinical sites and eventually, as patient outcome data become available, to apply quantitative advanced modeling tools to identify predictive signatures of cell properties that correlate with efficacy and safety. When feasible, synovial fluid will be aspirated for cell characterization.

## **4.0 Study Design**

### **4.1 Overall study design**

We propose a multicenter prospective single-blinded randomized controlled clinical trial to test the safety and efficacy of autologous bone marrow (BMAC), adipose tissue (ADP), and third party human mesenchymal stem cells manufactured from umbilical cord tissue (UCT) to a current standard, corticosteroid injections (CSI), for the treatment of Knee Osteoarthritis. The study will include a parallel design using a blocked central randomization scheme of 1:1:1:1 (BMAC:ADP:UCT:CSI).

Subjects, who have provided written informed consent and are determined to be eligible, will be randomized to one of the following arms and treatments.

**Arm 1** includes randomization to bone marrow derived MSCs versus corticosteroid injection.

**Arm 2** includes randomization to adipose derived MSCs versus corticosteroid injection.

**Arm 3** includes randomization to umbilical cord tissue MSCs versus corticosteroid injection.

Subjects randomized to Arm 1 or Arm 2 will undergo a procedure (bone marrow aspiration or liposuction) but will only receive one of the possible injections. For instance, subjects randomized to the control portion of Arm 1 will undergo a bone marrow aspiration but will receive a blinded corticosteroid injection. The bone marrow aspirate will be processed and utilized for cell characterization.

The corticosteroid cohort will serve as the control group for the trial. An injection of normal saline and Depomedrol will be used in a standard agreed upon preparation as described in the Operations Manual.

Two of the MSC preparations, adipose tissue and bone marrow, will be derived from autologous tissues and the third will be derived from a third party, unrelated allogeneic donor human umbilical cord tissue. The autologous products will be processed at the point of care and delivered without cryopreservation.

The allogeneic cord tissue MSC product will be manufactured and cryopreserved at the GMP cell manufacturing laboratory at Duke University Medical Center. This product will be shipped to the study sites in the cryopreserved state and thawed immediately prior to administration at the site. In all cases, the product administered to the subject will be characterized with cell counts, viability, sterility cultures, flow cytometry or mass cytometry and functional assays.

In order to accurately assess the efficacy of these treatments, routine follow-up examinations will be necessary. Follow-up exams will occur at intervals of 1 week, 1 month, 3 months, 6 months, 9 months (telephone only) and 1 year. After completing the screening and consent portion of the trial, the subjects will undergo a pre-injection MRI and then an additional MRI at 6 and 12 months. Additionally, subjects will fill out PROs at each time point.

The Marcus Center for Therapeutic Cell Characterization and Manufacturing (MC3M) at Georgia Institute of Technology will serve as a core cell analytics center for this clinical trial. MC3M's goal is to provide deep and broad characterization of all cells used in the trial, including synovial fluid, harmonize and standardize analytical and processing parameters across the different clinical sites and eventually, as patient outcome data become available, the MC3M will apply quantitative advanced modeling tools to identify predictive signatures of cell properties that correlate with efficacy and safety.

#### **4.2 Scientific Rationale for Study Design**

The current treatment of osteoarthritis relies on joint stability and non-operative control of inflammation. Oral non-steroidal anti-inflammatory (NSAID) options remain the initial line of treatment. When oral NSAIDs have failed, treatments with intra-articular

injectable corticosteroids for local pain management have proven successful for a short period of time, though evidence exists that their long-term use can be detrimental.

Other non-surgical treatment options include the injection of hyaluronic acid or other gels and biologics such as platelet rich plasma. While these treatments do provide pain relief, their precise mechanism of action is not known.

Joint arthroplasty is a definitive and successful surgical intervention typically offered to age appropriate patients after other less invasive measures have failed. However, this is substantial surgical intervention and possesses the inherent risks of any such procedure. Concern also exists regarding the longevity of knee arthroplasty, particularly in the younger, more active population.

Cell therapies have been increasingly employed to treat osteoarthritis, which include various forms of autologous (harvested from the same patient's body) mesenchymal stem cell injections. However, while this procedure has shown better outcomes than other non-surgical treatments, questionable reproducibility and the limited supply of stem cells limits the potential improvements to this valuable technique.

A large case series (41 subjects, 75 knees) with different biologics injections, most of which were autologous bone marrow concentrate (BMAC) + adipose derived stromal vascular fraction (SVF) were injected into the knee joint. Visual analog score (VAS), knee injury and osteoarthritis score (KOOS), international knee documentation committee (IKDC) and Lysholm knee Scores (patient reported outcome measures, PRO's) were all improved in the treated group [1]. ***Better outcomes were noted in those with lower degrees of osteoarthritis.***

Recently, a well-designed small clinical (proof of concept) trial was done with 2-year follow-up, evaluating different dosages of adipose derived SVF which were cultured and injected for the treatment of knee osteoarthritis. What made this study interesting was that it examined small, medium, and high doses of MSCs and evaluated their effects using MRI, arthroscopy, and clinical outcomes [2]. ***However, there was no control group and the study did not have a large number of subjects.***

Another study investigated a control group (saline) compared to same day BMAC preparation (non-expanded). The cells were characterized and the injections were done on bilateral knees with one knee getting the control and one getting the BMAC. The results showed marked improvement in symptoms but it was not statistically different between the two groups secondary to under powering of the study [3]. ***The fact that saline control also showed a good outcome indicates that such study was not well controlled and more rigorous studies with an unbiased approach throughout several recruiting sites is needed.***

There is an urgent need to establish which cell based therapy will yield sustained and reproducible treatment for osteoarthritis. We believe that the cell source is a key

determinant of the success of the MSC injections into the knee joint to alleviate pain and immediately enhance function and even halt the natural progression of the diseases.

### **4.3 Enrollment**

Subjects will be enrolled after the investigator has completed the following: confirm the subject has signed the informed consent and Health Insurance Portability and Accountability Act (HIPAA) Authorization, all screening assessments have been completed, and confirm that the subject has met all the inclusion criteria and none of the exclusion criteria.

Randomization can occur at any time after confirmation that the subject meets eligibility, but should occur within 30 days of the date of informed consent form signing. If the period is more than 30 days, an updated informed consent process must take place.

Enrollment of subjects is expected to last approximately 13 months in order to obtain the numbers needed. An additional three months has been incorporated into the study to allow for unanticipated delays and potential protocol changes.

### **4.4 End of Study Definition**

A subject is considered to have completed the study if he/she has completed all phases of the study including the one-year follow-up visit. The end of the study is defined as the date of the last visit of the last subject in the study shown in the Schedule of Activities for the last subject in the trial.

Final data analysis will occur following completion of study activities.

### **4.5 Study Stopping Rules**

If one of the following safety issues occurs, further enrollment will be halted until the Medical Monitor, [name], reviews all available data and makes recommendations as to the next steps:

- Any potential related serious adverse event (SAE).
- Other findings that, at the discretion of the study team, DSMB, investigator and/or Medical Monitor, indicate that the study should be halted.

## **5.0 Study Population**

### **5.1 Eligibility Criteria:**

The following is a list of stringent inclusion and exclusion criteria that is designed to reduce confounding and conflicting variables while studying the effect of biologic injections for knee osteoarthritis.

#### **5.1.1 Inclusion Criteria**

1. Age  $\geq 40$  but  $\leq 70$  years old
2. Males and Females

3. Recent knee radiograph of the targeted knee (standing AP lateral and sunrise view)
4. Diagnosis of OA in the targeted knee (radiographic evidence of OA in the medial and/or lateral tibiofemoral compartment, which would include one or more osteophytes on a standard radiograph taken within 3 months). Subjects may have concomitant patellofemoral but they must have grade II or higher medial or lateral tibiofemoral knee OA and the primary pain must be related to the tibiofemoral arthritis.
5. Continued OA pain in the targeted knee despite conservative measures (per treating provider's discretion)
6. Average daily VAS  $\geq 3$
7. Kellgren-Lawrence system of Grade II, III, or IV
8. Females of childbearing potential (FCBP) only, must have a negative pregnancy test done at screening prior to enrollment. FCBP is defined as any premenopausal female unless they have had a surgical sterilization procedure including, but not limited to, hysterectomy, tubal ligation or oophorectomy.
9. Women and men of child-producing potential must agree to use acceptable contraception methods for the duration of the trial such as birth control pills or condoms with spermicide.

### **5.1.2 Exclusion Criteria**

1. Clinically apparent tense effusion of the targeted knee
2. Significant valgus/varus deformities (+/- 10 degrees)
3. Viscosupplementation within 6 months in the targeted knee
4. Other Biologic Injection (PRP or stem cell) within 1 year in the targeted knee
5. Surgery in the targeted knee within the past 6 months (either open or scope)
6. Systemic or intra-articular injection of corticosteroids in any joint within 3 months before screening
7. Daily opioid use for the past three months
8. History of malignancy in the previous 5 years prior to study entry, with the exception of in-situ cancers treated only by local excision with curative intent.
9. History of, or ongoing, autoimmune disorder that requires treatment with an immunosuppressive medication
10. Active, suspected, or prior infection to the joint in the targeted knee
11. Part of a vulnerable population per Office for Human Research Protections (OHRP) definition (pregnant women and breast-feeding women, cognitively impaired, prisoners, etc.)
12. Unwilling to discontinue the use of Non-Steroidal Anti-Inflammatory (NSAID)s for 7 calendar days prior to the procedure

13. Unwilling to discontinue use of NSAIDs for 5 calendar days after procedure
14. History of bleeding disorders or inflammatory joint disease
15. Inability to hold anti-platelet therapy according to treating provider prior to procedure
16. Subject is, in the opinion of the investigator, unable to comply with the requirements of the study protocol or is unsuitable for the study for any reason.
17. Uncontrolled diabetes (determined by the treating investigator)
18. Subject has an active workers' compensation case in progress with targeted knee
19. Subject with insufficient amount of subcutaneous tissue, at the discretion of the treating investigator, upon examination
20. Hemoglobin less than 10g/dL at the time of screening
21. Leukocytes <3,000/ $\mu$ L; neutrophils <1,500/ $\mu$ L; lymphocytes <800/ $\mu$ L; platelets <100,000/ $\mu$ L at the time of screening
22. Diagnosis of liver disease as defined by alanine aminotransferase (ALT) >3x the upper limit of age-determined normal (ULN) or total bilirubin > 1.5x ULN
23. Subjects who have had greater than 3 corticosteroid injections in the targeted knee in the 12 months prior to screening or at the physician's discretion.
24. Subjects with a known diagnosis of osteoporosis.
25. Subjects with anticipated use of systemic corticosteroids during the study period for treatment of a chronic medical condition.

